7.3 Recruitment method

Recruitment efforts will take place only during the recruitment phase. All advertisements will be removed once recruitment is complete. We may post flyers at various local businesses (e.g., libraries, stores, and restaurants) every few months during the recruitment phase, post website advertisements at the beginning of recruitment and remove the ads when recruitment is completed, and contact individuals through research recruitment services. We may make up to 3 attempts to contact participants from the companion study by email and/or phone with a brief description of the opportunity. We may contact individuals from the Center for Healthy Minds Participant Registry one time via email with information about the research opportunity.

7.4 Recruitment materials

We will use email advertisements, flyers, research recruitment services, and website advertisements to inform potential participants about the study. Recruitment will occur on a continuous basis during data collection.

7.5 Compensation

We will pay participants by sending checks or prepaid debit cards in the mail. Participants will be paid twice during the study – once after completion of the Week 4 Activities and again after

completion of the 3-Month Follow-Up. If participants choose to withdraw or are withdrawn by the study team, they will receive payment for the study components that they completed.

Participants will be compensated up to \$150 for participating in the study as follows:

- Initial (Pre-Intervention) Activities = \$10
- Week 1 Activities = \$10
- Week 2 Activities = \$10
- Week 3 Activities = \$10
- Week 4 (Post-Intervention) Activities = \$25
- 3-Month Follow-Up = \$45
- Daily Movement (Location Tracking; must provide at least 60 days of valid data) = \$10
- Bonus for Completing All Study Procedures = \$30

8.0 Consent/Assent Process

8.1 Informed consent process

To obtain consent we will follow HRP-090 - SOP - Informed Consent Process.

Online Eligibility Survey Consent Process: Research candidates will be provided with an Information Sheet prior to completing the Online Eligibility Survey in REDCap. After reading the Information Sheet, research candidates will check a box to indicate that they have read the information and would like to continue with the survey. Survey data will be stored on REDCap and on a password-protected secure server.

Consent Process:

- 1. We will email (or mail, upon request) a consent form to research candidates who are potentially eligible for the study after completing the Online Eligibility Survey. We will ask participants to review the consent form prior to completing the Phone Screen (for MRI substudy participants) or Study Consent Call (for non-MRI substudy participants).
- 2. Eligible research candidates will be consented over the phone or via a web conferencing tool (e.g., Zoom) either during a Study Consent Call or immediately after the Phone Screen by trained research staff (i.e., principal investigator, study coordinator, or research assistant). We will recommend that participants complete the Phone Screen and/or informed consent process in a private room, if possible. If eligibility is not established upon completion of the Phone Screen, we will set up a separate time to call participants over the phone or by web conference to complete the informed consent process once eligibility is determined.
- 3. During the Study Consent Call, we will verify the research candidate's identity, review the consent form, and ask the research candidate if they have any questions or need further clarification about any aspects of the study. We will let research candidates know that they do not need to make a decision about participation right away, but can let us know once they have decided. We will inform research candidates that participation is voluntary and that they can stop at any time or skip any portion of the study that they do not feel comfortable completing. We will ensure that participants know who to contact if they have questions or concerns about the study in the future. We are requesting a waiver

- of signed consent for both the non-MRI and MRI substudies. If a research candidate chooses to continue with participation, we will document that the participant has given oral consent prior to starting study procedures.
- 4. If circumstances arise that make it necessary to obtain re-consent of research participants (e.g., substantive changes in the research, significant new findings), we will email the updated consent form with changes highlighted to the participant and explain the changes either over the phone or via a web conferencing tool (e.g., Zoom. We will ask participants if they have any questions/concerns. If they would like to continue in the study, we will document that the participant has given oral consent prior to continuing with the study.

8.2 Altering elements of consent

We are requesting an altered consent process and waiver of signed consent for the Online Eligibility Survey and Phone Screen, which present no more than minimal risk of harm to subjects and involve no procedures for which written consent is normally required outside of the research context. The Online Eligibility Survey and Phone Screen will be used to determine if research candidates are eligible for the study. The forms ask questions for screening purposes only, such as age, English proficiency, meditation experience, general health issues, and psychiatric symptoms.

The Online Eligibility Survey could not be carried out without the waiver because meeting with all research candidates who respond to our ads to obtain written informed consent would not be practical. Also, providing more information may decrease understanding of consent information and/or reduce study enrollment. If we provided all elements of consent in the Online Eligibility Survey, research candidates may not read all the information and be uninformed, or they may not sign up for the study at all. We would like to provide the essential elements of consent while reducing subject burden as much as possible.

We are requesting a waiver of signed consent for the study, which presents no more than minimal risk of harm to subjects and involves no procedures for which written consent is normally required outside of the research context. We will provide participants with a long form consent document that they can review and keep, complete a Study Consent Call over the phone/Zoom, and obtain oral consent, which we will document in our records prior to starting study procedures.

9.0 Process to Document Consent in Writing

9.1 Documentation of consent

Because this is a remote study, we will not follow HRP-091 - SOP - Written Documentation of Consent. Participants will not provide written consent. Instead, they will provide oral consent over the phone/Zoom, which we will document on the Oral Consent Script.

9.2 Waiver of written documentation of consent

We are requesting a waiver of signed consent for the Online Eligibility Survey and Consent Form, which present no more than minimal risk of harm to subjects and involve no procedures for which written consent is normally required outside of the research context.

For the Online Eligibility Survey, research candidates will be provided with an Information Sheet in REDCap prior to completing the survey. After reading the Information Sheet, research candidates will check a box to indicate that they have read the information and would like to continue with the survey.

We will provide participants with a copy of the consent form and will obtain oral consent over the phone/Zoom prior to starting study procedures. We will document that the participant has provided consent on the Oral Consent Script.

10.0 Setting

10.1 Location

Research procedures will be performed remotely and at the Center for Healthy Minds.

11.0 Study Intervention

11.1 Description

The study intervention is the Healthy Minds Program (HMP), a 4-week mobile health meditation training program. HMP was developed by our affiliated non-profit, Healthy Minds Innovations, Inc. Participants in the intervention group will download a study-specific version of the HMP app to their smartphone and complete the 4-week program. Participants in the waitlist control group will be given the opportunity to use the HMP app upon completion of the study.

12.0 Study Timelines

12.1 Study timeline

Participants will be involved in the study for approximately 4-5 months. Recruitment will start upon UW Institutional Review Board (IRB) approval and continue until study goals are reached. We estimate that we will complete the study, including primary analyses, in approximately 3 years.

13.0 Procedures Involved

13.1 Study design

This will be a two-group randomized controlled trial assessing the impact of the Healthy Minds Program (HMP), a meditation-based well-being app, on behavioral and self-reported outcomes associated with stress and well-being in 150 individuals. Participants will be adults ages 25 to 65

years who have no significant experience with meditation, have access to a smartphone, and are willing to follow through on all aspects of the protocol. The primary endpoint will be scores on the perceived stress scale. Participants will be randomized to the HMP or waitlist control group at a 2:1 ratio. Prior to randomization, participants will complete initial surveys and a computerized task remotely. Participants assigned to the HMP group will complete a 4-week well-being program remotely using an app on their smartphone. Each week participants will also complete a set of online surveys/tasks. Waitlist control participants will also complete the online surveys/tasks each week for 4 weeks. All participants will complete a final set of follow-up surveys/tasks 3 months later. In addition, we will track participant location using GPS smartphone technology throughout the study.

13.2 Schedule of study procedures

13.2 Schedule of study proce	dures			4-W Interv		
Study Procedure/Activity	Web Screen	Phone/ Zoom Call	T1	T2-T4	T5	Т6
Consent via Information Sheet	X					
Screening Questions	X					
Review Eligibility	X					
Informed Consent Process for		X				
Main Study						
Payment Information Survey		X				
Payment Information Update						X
Survey						
Intervention (i.e., Healthy				X^1	X^1	
Minds Program)						
Behavioral Pattern Separation			X		X	X
Task						
Attention Check Items			X		X	X
Behavioral Risk Factor			X			
Surveillance System (BRFSS)						
Adverse Childhood						
Experiences (ACE) Module						
Demographics			X			
Demographics & Meditation			X			
Experience						
Determinants of Meditation			X			
Practice Inventory-Revised						
(DMPI-R)						
Digital Working Alliance				X^1	\mathbf{X}^1	
Inventory (DWAI)						
Feedback Survey			X	X	X X	X
Five Facet Mindfulness			X		X	X
Questionnaire (FFMQ),						
Awareness Subscale						
Flourishing Measure			X		X	X
Global Physical Activity			X		X	X
Questionnaire (GPAQ)						

Healthy Minds Index		X		X	X
(HMIndex)					
Mainz Inventory of		X		X	X
Microstressors (MIMIS)					
Marlowe-Crowne Social		X			
Desirability Scale (MCSDS)					
Mindfulness-Based Program -				X^1	
Meditation-Related Adverse					
Effects Scale (MBP-MRAES)					
Mindfulness Adherence			X^1	X^1	X^1
Questionnaire (MAQ)					
NIH Toolbox Loneliness		X		X	X
Pre- & Post-Practice Items			X	X	
PROMIS Item Bank -	X	X	X	X	X
Emotional Distress - Anxiety					
(Computer Adaptive Version)					
PROMIS Item Bank -	X	X	X	X	X
Emotional Distress -					
Depression (Computer					
Adaptive Version)					
PROMIS Item Bank -		X	X	X	X
Emotional Distress - Sleep					
Disturbance (Computer					
Adaptive Version)					
Perceived Stress Scale (PSS)		X	X	X	X
PTSD Checklist (PCL-5)		X		X	X
Location Tracking with		X^2	X^2	X^2	X^2
Passive GPS ⁴					
Debriefing Form					X

¹HMP group only

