3.3 Primary and secondary study endpoints

Primary endpoints

• Scores on the perceived stress scale at post-intervention (T5) controlling for baseline (T1)

Secondary endpoints

- Performance on the behavioral pattern separation task (post-intervention and follow-up/T6)
- PROMIS depression and anxiety (post-intervention and follow-up)

Tertiary and exploratory endpoints

- Symptoms of PTSD measured using the PCL-5 (post-intervention and follow-up)
- PROMIS sleep disturbances (post-intervention and follow-up)
- Five-facet mindfulness questionnaire, awareness subscale (post-intervention and follow-up)
- NIH toolbox Loneliness (post-intervention and follow-up)
- Healthy Minds Index (post-intervention and follow-up)
- Real-world experiential diversity measured using continuous GPS location tracking (Measured continuously throughout study participation)
- Trajectories of change for self-report outcomes assessed on a weekly basis

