HMP group participants will be instructed on downloading and installing a study-specific version of the HMP app. The 4-week meditation program will take approximately 60 minutes to complete each week. The program will be self-paced and completed remotely. While completing the HMP each week, participants will listen to podcast-style lessons in the app to learn about meditation from scientists and experts in well-being. The app will also guide participants through seated and active meditations. Participants may have the option to provide demographic and meditation experience information and complete the Healthy Minds Index questionnaire to assess their current level of well-being within the app. The app will collect activity data (e.g., when, how long, and what content was listened to), device type, and GPS data (if enabled by the participant). Participants will also occasionally answer pre- and post-practice questions. The app will not collect any identifying information. Participants will have the option to continue using the HMP app after completing the 4-week program. If they choose to do so, we will continue to monitor their app usage and any other data collected through the HMP app throughout the study to learn more about its long-term impact on well-being. The HMP app is considered an FDA regulated device that should qualify as a "non-significant risk (NSR) device". We are seeking an NSR determination and have, therefore, uploaded an NSR request letter in ARROW (see Drug and Device Documents section, #2 Device Documentation).

Timepoints 2-5 - During & Post-Intervention Activities: HMP group participants will complete online measures (see section **13.2 Schedule of study procedures**) remotely through REDCap for Timepoints 2-5 during the same weeks as the 4-week intervention. The measures will take 10 to 45 minutes to complete each week. Waitlist participants will also complete most of the same measures over 4 weeks. Participants will have approximately one week to complete each set of self-paced activities.

Timepoint 6 - 3-Month Follow-Up: About three months after Timepoint 5, participants will complete a final set of measures (see section **13.2 Schedule of study procedures**) remotely online through REDCap, which will take 30 to 45 minutes.

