13.5 Long-term follow-up

There are no current plans for long-term follow-up other than Timepoint 6 (3-Month Follow-Up), which is part of the research procedures listed above. For those in the HMP group, we will continue to use any data collected through the HMP app (e.g., usage data) until Timepoint 6. Additional follow-up activities may be planned by study personnel and/or collaborators. The consent form includes a section where participants can opt in to future contact.

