23.0 Provisions to Monitor the Data to Ensure the Safety of Participants

23.1 Data and safety monitoring plan

Adverse events will be tracked (including details of the incident, actions taken, and follow-up steps) by study staff and reported to the PI. The PI will be responsible for the monitoring and reporting of adverse events, as necessary, to the IRB.

Other notable incidents that occur during recruitment, consent, or data collection that are determined to be unexpected and related to the study procedures will be reported in a detailed log on an annual basis (at the time of continuing review). The PI will be responsible for informing the IRB immediately of any life threatening incidents as well as take appropriate action to stop the study, release a participant from the study, or modify procedures to reduce and/or eliminate the occurrence of the risks.

The PI will review information on adverse events, protocol deviations, data quality, participant recruitment, accrual, and retention (including reasons for dropout), whether all participants met inclusion criteria, and demographics. This information will be provided in biannual reports to an Independent Monitor who will make recommendations regarding the safe continuation of the study and whether any changes to the protocol are needed to ensure participant safety. Once annually the Independent Monitor will forward an approved report to the UW Health Sciences IRB and NIMH.

Given the safety and risk level of the intervention and study procedures, we cannot anticipate any conditions that would trigger an immediate suspension of the research.

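### The only meditation-specific harm scale is given once, at T5, to the HMP group and is not repeated at T6, although app use may continue and is followed to T6.

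*Combined protocol and SAP*

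**What the plan says.** Section 13.2 schedules the "Meditation-Related Adverse" Effects Scale in the T5 column only, with a footnote restricting it to the HMP group. In the same table the "Mindfulness Adherence" Questionnaire goes to that group at T2-T4, T5 and T6.

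Section 13.3 says: "Participants will have the option to continue using the HMP app after completing the 4-week program". For those who do, usage is monitored for the rest of the study to see how the app affects well-being over the longer run. Section 13.5 repeats this for the HMP group: "we will continue to use any data collected through the HMP app (e.g., usage data) until Timepoint 6". On timing, section 13.3 says: "About three months after Timepoint 5, participants will complete a final set of measures".

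Other safety-relevant collection runs to T6. Section 23.1 says: "Adverse events will be tracked (including details of the incident, actions taken, and follow-up steps) by study staff and reported to the PI". It sets no limit by arm or timepoint, and adverse event information goes twice a year to an Independent Monitor. Section 3.3 lists "PROMIS depression and anxiety (post-intervention and follow-up") as secondary endpoints and "Symptoms of PTSD measured using the PCL-5 (post-intervention and follow-up") as exploratory. Section 13.2 gives these scales, PSS and PROMIS sleep disturbance to both arms at T5 and T6.

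The MBP-MRAES is not an endpoint in section 3.3, and section 20 describes no final harms summary.

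**The concern.** The plan follows continued practice for about three months after the programme ends, through app logs and a repeated adherence questionnaire, because it wants to learn about longer-run effects. It asks about meditation-related adverse effects only when the programme ends. An effect that first appears, or persists, during voluntary practice after T5 would reach the data only if a participant volunteers it, if staff happen to record it, or if it shows as a shift on a general symptom scale.

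Assessments are remote (section 6.1), and section 23.1 gives no method or schedule for eliciting events, so nothing in the documents replaces a direct question at T6. What is at stake is how complete the trial's account of tolerability is for continued use. The efficacy conclusions are not affected.

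**Working it through.** The plan gives no figure on this point to reproduce. The check is a reading of the schedule plus simple arithmetic.

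**1. Column position.** The PROMIS Anxiety row in section 13.2 fills all five cells: screening, T1, T2-T4, T5 and T6. Set against it, the single MBP-MRAES mark falls at T5. The adherence row has three marks: T2-T4, T5 and T6. Both rows are footnoted as HMP only.

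**2. What is followed after T5 in the HMP group.**

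| Item | T5 | T6 |
|---|---|---|
| App usage | yes | yes, to T6 |
| Adherence questionnaire | yes | yes |
| MBP-MRAES | yes | no |
| PSS, PROMIS, PCL-5 (both arms) | yes | yes |
| Adverse event tracking (both arms) | no cut-off stated | no cut-off stated |

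The MBP-MRAES is the one line that stops.

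**3. Calendar time after the only administration.** Inputs: a 4-week programme with T5 at its end, and T6 about three months later, taken as 12 to 13 weeks.
- 12 / (4 + 12) = 0.75
- 13 / (4 + 13) = 0.76

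**4. App exposure after T5.** The documents do not give it. The assigned programme is about 60 minutes a week for 4 weeks, so 4 × 60 = 240 minutes if completed in full (an assumption). Let u be mean weekly minutes of use after T5, averaged over the HMP group, for 13 weeks. The share of use after T5 is 13u / (240 + 13u).
- u = 0: 0%
- u = 15 (a quarter of programme pace): 195 / 435 = 45%
- u = 60 (full programme pace): 780 / 1020 = 76%

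With 12 weeks the last two become 180 / 420 = 43% and 720 / 960 = 75%. These values of u are illustrations; the result depends entirely on uptake.

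**5. What a T6 administration could show.** 150 × 2/3 = 100 are assigned to HMP, and 10% dropout leaves about 90. If none of 90 reported a given effect, the one-sided 95% upper bound on its rate would be 1 − 0.05^(1/90) = 3.3%. The bound is wider among continuing users, who are fewer.

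**6. Limits of a worsening cut-off.** Section 20.2 cites 0.5 SD as a minimal important difference for the PSS only. If scores are normal with equal SDs and no true mean change, the change score has SD √(2(1 − r)) in baseline SD units, where r is the correlation between timepoints. The share worsening by at least 0.5 SD by fluctuation alone is P(Z > 0.5 / √(2(1 − r))).
- r = 0.5: P(Z > 0.50) = 31%
- r = 0.7: P(Z > 0.65) = 26%
- r = 0.8: P(Z > 0.79) = 21%

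These correlations are assumptions. A raw proportion worsening therefore says little, and only the difference between arms is informative.

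**The case against.** The strongest defence is that the scale is given at the end of the assigned intervention, which is where it matters most. The protocol describes the study as minimal risk. Section 13.2 marks the intervention through T5 and not at T6, use after that is voluntary, and other safety collection continues. On this view a second administration is a preference. Much of that stands, and it keeps the point small.

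Several stronger readings are tempting, and the documents do not support them.

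- **Continued use is expected.** Section 13.3 makes it optional.
- **Harms after T5 go uncollected.** Section 23.1 tracks adverse events without a T5 cut-off, section 22.6 sends disclosed suicidal ideation or self-harm to clinical staff without a time limit, and the symptom scales are repeated at T6.
- **Harms have no control comparison.** This is true of the MBP-MRAES only. PSS, PROMIS and PCL-5 are measured in both arms at T5 and T6. By its name the scale concerns effects of meditation, and waitlist participants get the app only after the study. If its items ask about effects attributed to practice (an assumption, since the item wording is not given), one-arm use belongs to the scale.
- **Three quarters of exposure is missed, so the Independent Monitor sees little of it.** The fraction is calendar time, and the adverse event information sent to the monitor is not confined to four weeks.
- **Event counts by arm are biased.** Section 20 plans no such comparison. The elicitation method is unstated, which is missing detail and not evidence of bias.

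What the defence does not answer is why adherence is worth asking about at T6 in this group and adverse effects of the same practice are not.

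**Conclusion.** The point holds in a limited form. After T5, adverse effects of meditation are not systematically elicited with the one scale chosen for that purpose, while continued practice is allowed and measured to T6. About 75% of calendar time from intervention start to T6 (75% to 76%, taking three months as 12 to 13 weeks) follows the only administration. The corresponding share of app exposure cannot be derived: it is near zero if few continue and substantial if many do.

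The conclusion assumes that a single question at T5 cannot capture effects that begin later, which follows from timing alone. It does not depend on the scale's recall window, which the documents do not give. This is a cheap improvement to harm ascertainment and not a flaw in the trial's main inference.

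**What to change.** Add the MBP-MRAES at T6 for the HMP group in the section 13.2 schedule, with instructions that refer to the period since T5. State in section 20 that the T5 and T6 responses will be reported descriptively, with T6 shown beside T6 adherence and app usage so that reports can be read against actual continued use.

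The cost is an amendment and a few extra minutes for HMP participants in a survey that now takes 30 to 45 minutes. Participants already past T6 would lack the item, so the report should give the number who were asked. If T6 collection is complete, state the gap as a limitation.

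Optionally, and at no cost in data collection, add a descriptive between-arm summary of worsening from T1 on PSS, PROMIS anxiety, PROMIS depression and PCL-5 at T5 and T6. State any cut-off as an assumption, since the plan cites 0.5 SD for the PSS only, and read the result only as a difference between arms.
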